6.5 CONCOMITANT THERAPY

All subjects in this study are asked to continue their standard of care (SOC) treatment for CD as prescribed by their treating gastroenterologist.

For this protocol, a prescription medication is defined as a medication that can be prescribed only by a properly authorized/licensed clinician. Medications to be reported in the Case Report Form (CRF) are concomitant prescription medications (e.g. antacid medication, including additional clinically indicated antibiotics or anti-fungals), over-the-counter medications and supplements.

Patients taking over-the-counter prebiotics and/or probiotics will be counseled by their treating gastroenterologist at the time of enrolment and recommended to stop taking pre/probiotics by the week 0 study visit, and to refrain from using probiotics for the duration of the study (Week 52). If patients choose to continue using pre-and/or pro-biotics, this will be recorded on the CRF.

6.5.1 RESCUE MEDICINE

Not applicable.

7 STUDY INTERVENTION DISCONTINUATION AND PARTICIPANT DISCONTINUATION/WITHDRAWAL

7.1 DISCONTINUATION OF STUDY INTERVENTION

Discontinuation of the antibiotic treatment between weeks 4 and 12 does not mean discontinuation of the study. A participant who discontinues the antibiotic intervention will be moved into the Group A control group (Group A1) and receive SOC, but these patients will not be included in the analysis of Group A1 to avoid selection bias as a patient who discontinues treatment in week 11 may differ from a patient who discontinued in week 5. Any patients discontinuing treatment will therefore be reported separately.

The remaining study procedures should be completed as indicated by the study protocol. If a clinically significant finding is identified (including, but not limited to changes from baseline) after enrollment, the investigator or qualified designee will determine if any change in participant management is needed. Any new clinically relevant finding will be reported as an adverse event (AE). Specific criteria for discontinuation due to known or potential AE associated with the study intervention are provided in section 7.2.

7.2 PARTICIPANT DISCONTINUATION/WITHDRAWAL FROM THE STUDY

Participants are free to withdraw from participation in the study at any time for any reason if they wish to do so without any consequences. An investigator may discontinue or withdraw a participant from the study for the following reasons:

- Pregnancy
- Significant study intervention non-compliance
- Occurrence of a clinical AE known to be associated with study intervention including new onset peripheral neuropathy, new onset seizures, new onset clinically significant leukopenia, new-onset QT prolongation, evidence of hepatotoxicity, allergic reaction. Criteria for stopping investigational therapy due to potential hepatotoxicity include any of the following laboratory abnormalities:
 - ALT or AST >8xULN
 - ALT or AST >5xULN for more than 2 weeks
 - ALT or AST >3xULN and (TBL >2xULN or INR >1.5)
 - ALT or AST >3xULN with the appearance of fatigue, nausea, vomiting, right upper quadrant pain or tenderness, fever, rash, and/or eosinophilia (>5%)

Should any of these laboratory abnormalities occur, the participant will discontinue investigational therapy and undergo appropriate evaluation for other causes of abnormal liver function tests. The participant must be followed until resolution or stabilization and the results of the evaluation for alternate causes of abnormal liver enzymes will be documented in the Reason for Withdrawal Case Report Form (CRF)

- If any other clinical adverse event, laboratory abnormality, or other medical condition or situation occurs such that continued participation in the study would not be in the best interest of the participant
- Disease progression which requires discontinuation of the study intervention
- If the participant meets an exclusion criterion (either newly developed or not previously recognized) that precludes further study participation

The reason for participant discontinuation or withdrawal from the study will be recorded on the Reason for Withdrawal CRF. Subjects who withdraw during the pilot study will try to be replaced.

7.3 LOST TO FOLLOW-UP

A participant will be considered lost to follow-up if he or she fails to return for 2 consecutive scheduled visits as well as the Week 52 follow-up visit, and is unable to be contacted by the study site staff.

The following actions must be taken if a participant fails to return to the clinic for a required study visit:

- The site will attempt to contact the participant and reschedule the missed visit and counsel the participant on the importance of maintaining the assigned visit schedule and ascertain if the participant wishes to and/or should continue in the study.
- Before a participant is deemed lost to follow-up, the investigator or designee will make every effort to regain contact with the participant (where possible, 3 telephone calls and, if necessary,

a certified letter to the participant's last known mailing address or local equivalent methods). These contact attempts should be documented in the participant's medical record or study file.

- Should the participant continue to be unreachable, he or she will be considered to have withdrawn from the study with a primary reason of lost to follow-up.

8 STUDY ASSESSMENTS AND PROCEDURES

8.1 EFFICACY ASSESSMENTS

History and Physical exam – These will be performed as per the standard of clinical care including height (height velocity), weight and perianal inspection. The primary outcome variable will be whether sustained remission at 52 weeks after starting standard of care induction therapy is achieved. Sustained remission is not defined by PCDAI alone; but rather by PCDAI ≤ 10 at week 52 AND not having need of re-induction for clinical flare (new course of EEN, need to start steroids), no steroid dependence, no biologic (anti-TNF) use, and no intestinal surgery by 12 months. As secondary outcome variables of efficacy, longitudinal (clustered and with respect to baseline) changes in disease activity indices components, and inflammatory markers in blood and stool, will be collected including the PCDAI score (0-100), normalization of CRP (<0.5 mg/dL or the local reference range as applicable), fecal calprotectin (microgram/g) and Delta-fecal calprotectin before and after the study intervention. In addition, longitudinal (clustered and with respect to baseline) changes of Patient-reported outcome will be collected (IMPACT (self-report, ages 9-17 years).

Blood samples – Blood samples will be drawn as per the standard of clinical care including erythrocyte sedimentation rate (ESR), C-reactive protein, albumin, alanine transaminase (ALT), aspartate transaminase (AST), bilirubin, Urea (Blood Urea Nitrogen (BUN) and Creatinine,)and complete blood count (including hematocrit). These blood results, provided by the local clinical labs, will be required to calculate the disease activity index and monitor for toxicity due to methotrexate.

Stool samples – For assessment of inclusion criteria for Screening, stool samples will be obtained for local testing for the presence of toxicogenic *C. difficile*. This sample may be a pre-consent sample collected as standard of care. Study stool samples will be collected at each study visit and split into two aliquots; one for Fecal calprotectin testing and one for microbiome analysis at the central laboratory Dalhousie University (Integrated Microbiome Resource) as coordinated from Amsterdam UMC.

Special assays - DNA sequencing and microbiome analysis: Identification of favorable vs unfavorable (Proteobacteria-rich) signature: the stool for analysis will be collected at baseline for screening (in children undergoing endoscopic investigations as decided by the responsible physician, stool will be obtained before the bowel prep for diagnostic endoscopy or starting from 48 hours after an endoscopy), in a dedicated kit (e.g. DNAGenotek) with solution buffer. Analysis of the V4-V5 16S region by a blinded bioinformatician (labelling the patients using Bayesian analysis (posterior probability $>30\%$ of carrying the Proteobacteria-rich, unfavorable signature) within 2-3 weeks, in order to allow participants to be randomized to either adjuvant antibiotics or no additional treatment, by the end of week 4 from baseline.

8.2 SAFETY AND OTHER ASSESSMENTS

Electrocardiograms (ECGs): ECG is for screening purposes only to identify prolongation of QT (QTc) corrected for age appropriate norms. If there is prolongation, as identified by each responsible physician, then the responsible physician is responsible for communicating this finding with the patient and family and arranging appropriate follow-up with cardiology. Patients found to have QT prolongation will not be treated with investigational therapy and appropriate guidance will be given regarding avoiding other medication with the potential of QTc prolongation (e.g. avoiding ondansetron). Further, all patients randomized to group A2 will receive a follow-up ECG 2-4 weeks after the initiation of the study drug to ensure that new-onset QT prolongation is not occurring as a result of azithromycin treatment. If clinically significant QT prolongation is detected at follow-up ECG, patients should discontinue investigational therapy. If the subject is not in clinical remission at week 4, then the responsible physician will decide whether azithromycin/metronidazole can be started as additional induction therapy.

Blood samples: Blood drawn as per the standard of clinical care will be tested for alanine transaminase (ALT), aspartate transaminase (AST), bilirubin, BUN and Creatinine by the local clinical labs to monitor for toxicity due to methotrexate.

Urine pregnancy tests: A urine pregnancy test will be administered at screening and repeated at week 4 prior to the initiation of methotrexate in post-menarcheal female patients. These tests will be used to prevent exposure of participants to potential embryotoxic/teratogenic effects of methotrexate. Counselling and reinforcement of these potential risks and the importance of pregnancy prevention will be included at every study visit. Post-menarcheal patients will be counselled about the use of birth control to prevent unplanned pregnancy while taking methotrexate during this study period.

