1.3 SCHEDULE OF ACTIVITIES (SOA)

Procedures	Visit 1 Screening ≤30 days prior to week 0	Visit 2 Week 0	Study Visit 3 Week 4	Study Visit 4 Week 12	Study Visit 5 Week 24	Study Visit 6 Week 36	Final Study Visit 7 Week 52
Informed consent	X						
Demographic data	X						
Medical history	X	X	X	X	X	X	X
Review inclusion/exclusion criteria	X	X					
Concomitant medication review	X	X	X	X	X	X	X
Physical exam (including height and weight)	X	X	X	X	X	X	X
Medication calendar distribution and teaching		X					
Blood sample ^a	X	X ^b	X	X	X	X	X
Calculate PCDAI score (0-100)	X	X ^b	X	X	X	X	X
Stool sample (16S rRNA)	X	X ^b	X	X	X	X	X
Stool sample (FCP)	X	X ^b	X	X	X	X	X
Stool sample (C. difficile infection testing) ^c	X						
Urine pregnancy test ^d	X		X				
Adverse event review and evaluation			X	X	X	X	X
Randomization			X				
ECG, if applicable ^e			X				
Administer antibiotic, if applicable			X				
Teaching for antibiotic medication calendar, if applicable			X				
Complete Case Report Forms (CRFs)	X	X	X	X	X	X	X
IMPACT (ages 9 and older)		X		X	X		X

A window of study timepoint +/- 5 days is allowed for all visits/questionnaires/sampling.

a: Includes hematology and clinical chemistry Albumin, C reactive protein (CRP), hematocrit (HCT), erythrocyte sedimentation rate (ESR), alanine transaminase (ALT), aspartate transaminase (AST), creatinine, and bilirubin. Total blood volume collected at each visit will be 5ml.

b: The timing of the Screening and Week 0 visits will depend on the start of therapy. Week 0 blood and stool samples will not be repeated if provided during the screening visit, provided that the stool samples were collected prior to bowel prep.

c: If performed for clinical indication, as per standard of care

d: Only applicable for post-menarchal female participants initiating methotrexate

Procedures	Visit 1 Screening ≤30 days prior to week 0	Visit 2 Week 0	Study Visit 3 Week 4	Study Visit 4 Week 12	Study Visit 5 Week 24	Study Visit 6 Week 36	Final Study Visit 7 Week 52
e: All patients randomized to group A2 and C will receive an ECG exam both prior to and at 2-4 weeks after the initiation of the study drug							

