5.2 EXCLUSION CRITERIA

An individual who meets any of the following criteria will be excluded from participation in this study:

1. Current or previous use of anti-TNF or other biologic therapy
2. Presence of stricturing, penetrating (intestinal or perianal) and/or fistulizing CD.
3. Pregnancy or lactation
4. Have undergone intestinal resection
5. Laboratory diagnosis of Clostridium Difficile Infection (CDI), if performed for clinical indication
6. Treatment with another investigational drug or other intervention within 30 days before week 0
7. Risk factors for arrhythmia including history of prolonged QTc, hypokalemia or hypomagnesemia, resting bradycardia, or concurrent treatment with other drugs with potential for QT prolongation.
8. History of Cockayne syndrome
9. Prior diagnosis of any hematologic condition/blood dyscrasia which may result in leukopenia (even if leukocyte count is normal at screening)
10. Known allergy or intolerance to azithromycin or metronidazole
11. Subjects who received IV anti-infective within 35 days prior to week 0 visit or oral anti-infectives within 14 days prior to the week 0 visit.
12. Subject on oral aminosalicylates who has not been on stable doses for greater than, or discontinued within, at least 14 days prior to week 0.
13. Subject on cyclosporine, tacrolimus or mycophenolate mofetil. Stable doses (no change within 14 days prior to week 0) of Azathioprine, 6-mercaptopurine or MTX are not a reason for exclusion.
14. Subject who received fecal microbial transplantation within 35 days prior to week 0 visit.
15. Screening laboratory and other analyses show any of the following abnormal results:
 - AST, ALT > 2 X upper limit of the reference range (as determined locally at each site)
 - Urea, Creatinine > 1.5X upper limit of the reference range (as determined locally at each site)
 - White blood cell (WBC) count < 3.0 X 10⁹/L
 - Total bilirubin >= 20 micromol/liter (1.17mg/dl); except for subjects with isolated elevation of indirect bilirubin relating to Gilbert syndrome
 - Hemoglobin < 80 gram/liter
 - Platelets < 100,000/ μ L

Note: The laboratory markers of e.g. AST and ALT are deliberately specified relative to upper limit of normal as these values (and units used) differ between the different labs within the USA and across the study sites in the USA, Canada and Europe.

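### Section 8.2 omits azithromycin-treated Group C from the follow-up ECG, and 6.5 and 8.2 state no QT-drug avoidance rule or week-4 re-check for treated children

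*Combined protocol and SAP*

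**What the plan says.** Exclusion criterion 7 (section 5.2) lists several arrhythmia risk factors, among them "concurrent treatment with other drugs with potential for QT prolongation". In the Schedule of Activities (section 1.3), the row "Review inclusion/exclusion criteria" is marked at screening and week 0 only. The row "Concomitant medication review" is marked at every visit, including week 4, when azithromycin starts.

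On ECGs, footnote e of the schedule reads "All patients randomized to group A2 and C will receive an ECG exam both prior to and at 2-4 weeks after the initiation" of study drug. Section 8.2 says that "all patients randomized to group A2 will receive a follow-up ECG 2-4 weeks after the initiation of the study drug" and does not mention Group C in that sentence. Its stopping sentence is "If clinically significant QT prolongation is detected at follow-up ECG, patients should discontinue investigational therapy", with no group named.

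On co-medication, 8.2 places the advice to avoid QT-prolonging drugs in its sentence on children already found to have QT prolongation: "Patients found to have QT prolongation will not be treated with investigational therapy and appropriate guidance will be given regarding avoiding other medication". Section 6.5 asks for concomitant medicines to be recorded and discourages pre- and probiotics, but says nothing about QT-prolonging drugs. Section 6.1.2 tells families to contact the coordinator about new emesis or significant nausea and allows a metronidazole dose reduction. It does not mention which antiemetics to avoid.

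**The concern.** The protocol treats a second QT-prolonging drug alongside azithromycin as reason enough to keep a child out of the trial. Once azithromycin starts, the sections that govern treatment do not carry that rule forward to the children who take it.

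The need for a rule is foreseeable. Section 2.3.1 says that most azithromycin side effects leading to discontinuation were gastrointestinal, nausea and vomiting included, and it puts nausea among the commonest metronidazole reactions. An antiemetic is a natural response, and the protocol's own example of a drug to avoid, ondansetron, is one.

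The follow-up ECG matters for the same reason. Group C takes the same azithromycin course as A2, so a site that works from the 8.2 narrative could leave out an ECG that the schedule requires. What is at stake is consistent safety cover for children treated at sites in several countries.

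**Working it through.** The plan gives no figure to reproduce. The check sets the texts side by side and adds simple date arithmetic.

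**1. Who gets the follow-up ECG.**
- Groups that may take azithromycin: A2 (section 4.1) and treated Group C (sections 4.1, 8.2 and 9.2) = 2 groups.
- Named in footnote e: A2 and C = 2 of 2.
- Named in the follow-up sentence of 8.2: A2 = 1 of 2.
- The two texts disagree for Group C. Footnote e matches exposure; 8.2 is incomplete. Both speak of children *randomized* to the group, which cannot apply to Group C because section 4.1 says these children are not randomized.

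**2. Who gets the avoidance advice.**
- Children with QT prolongation on the ECG: advised under 8.2, and not treated.
- Children without QT prolongation who start azithromycin: no advice stated in 8.2 or 6.5.
- Period without a stated rule: week 4 to week 12 = 8 × 7 = 56 days.

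**3. When the drug part of criterion 7 is last checked.**
- Scheduled eligibility reviews: screening and week 0 = 2, of which 0 fall at or after the start of azithromycin.
- Nominal gap from week 0 to week 4: 4 × 7 = 28 days.
- The schedule says "A window of study timepoint +/- 5 days is allowed for all visits/questionnaires/sampling". If week 0 is the fixed anchor and only the week-4 visit moves, the gap is 28 − 5 = 23 to 28 + 5 = 33 days. If both visits can move, it is 28 − 10 = 18 to 28 + 10 = 38 days.
- The protocol does repeat a check when a drug starts in another place: 8.2 repeats the pregnancy test at week 4 before methotrexate.

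**4. Whether the ECGs replace a drug rule.**
- The pre-dose ECG cannot show the effect of a drug added after it.
- The follow-up ECG falls 2 to 4 weeks into an 8-week course, so 8 − 4 = 4 to 8 − 2 = 6 weeks follow it with no further scheduled ECG.

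**5. What a medication review can and cannot check.**
- Criterion 7 also covers hypokalemia, hypomagnesemia and resting bradycardia. Potassium and magnesium are not in the blood panel listed in footnote a. A medication review can therefore re-check the drug part only.

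**The case against.** Much of this is already covered in practice. Week 4 has a medication review and, for A2 and C, an ECG before the first dose. A physician writes the prescription (section 6.3). Section 7.2 allows withdrawal when an exclusion criterion is newly met, and lists new-onset QT prolongation without limiting it to a group. A QT-prolonging drug started between weeks 0 and 4 should therefore come to light. All of this stands and lowers the weight of the point. It does not remove it: the 7.2 clause is permissive and schedules no check, the medication review has no action attached, and none of these steps tells a treated child's family or local doctor what to avoid in weeks 4 to 12.

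Several stronger readings are tempting, and the documents do not support them:

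- A reader might infer that Group C has no follow-up ECG. Footnote e requires one; the fault is a conflict between two texts.
- A reader might infer that the stopping rule does not reach Group C. The 8.2 sentence says patients, without limiting it to A2.
- A reader might infer that the cardiac-risk argument in 2.3.3 is contradicted. That argument rests on screening for rhythm abnormalities before antibiotics, which the pre-dose ECG does.
- A reader might infer that sites and families are never told. The package inserts, consent forms and Manual of Procedures were not available, so the finding covers only the protocol sections cited.
- A reader might infer that a week-4 check before allocation would by itself keep A1 and A2 comparable. It would not, because the ECG check still applies only after randomization to A2.

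**Conclusion.** The point holds as a safety gap of limited size in the protocol text. Section 8.2 names one of the two azithromycin groups for the follow-up ECG. It aims its avoidance advice at unexposed children, leaving a 56-day course with no rule stated in 6.5 or 8.2. The drug part of criterion 7 is last formally due 28 days before the first dose (23–33 or 18–38 days, depending on how the visit windows are read).

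The number of children concerned is not estimated. The documents give neither a rate of QT-prolonging co-medication nor a rate of non-remission at week 4, and treatment in Group C is left to the physician in 8.2 and 9.2. No effect on the comparison of A1 with A2 is claimed. The conclusion assumes that sites act on the protocol sections as written and that the unseen attachments do not already supply the rule.

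**What to change.** 1. Amend 8.2 so that the follow-up ECG covers every child treated with azithromycin (A2 and treated Group C), in line with footnote e. In both places replace *randomized to* with *treated with azithromycin*.
2. Give the 8.2 avoidance guidance to every azithromycin-treated child. State it for weeks 4 to 12 in 6.5, and repeat it in the 6.1.2 contact route for nausea or emesis. The sponsor should choose which drugs to list.
3. Use the medication review already scheduled at week 4 to check for QT-prolonging co-medication before any A2 or C dose. Stop or substitute the drug where possible; otherwise do not dose. Do this review before allocation where practical, but do not add a rule that bars allocation. Such a rule would lower the proportion successfully randomized, which the Netherlands addendum uses as a primary feasibility outcome, and would also withhold allocation from children who would have gone to A1. Keep every randomized child in the ITT set, dosed or not.

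The cost is protocol wording and one check inside an existing visit. It needs no new visit or sample, and no ECG beyond what footnote e already requires. The downside is a narrower choice of antiemetic for 8 weeks and, probably rarely, a child who is not dosed.
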